12 STATISTICAL ANALYSIS

This section presents a summary of the principal features of the planned statistical analyses. Statistical analysis details will be provided in the statistical analysis plan (SAP), and clinical pharmacologic analysis details will be provided in the clinical pharmacology analysis plan (CPAP), both of which will be finalized before clinical database lock.

12.1 Sample Size and Power

The primary efficacy endpoint is the change from baseline in the weekly average of the daily pain intensity on an NPRS at Week 12. The primary analysis will be a within-group comparison (i.e., change from baseline) in any VX-548 dose group.

The sample size is based on the primary analysis of the primary endpoint. With 37 evaluable subjects in the VX-548 high or mid dose group and 18 evaluable subjects in the VX-548 low dose group, there is more than 90% power in any VX-548 dose group to detect a mean change from baseline of 3 with a single group *t*-test at the 2-sided 0.05 significance level, assuming the SD is 2.3. With an evaluable sample size of 37, a 2-sided 95% CI for the mean change from baseline in the high or mid dose group will extend 0.77 on either side of the observed mean, assuming the CI is based on the *t*-statistic and the observed SD is 2.3. Under the same assumptions and an evaluable sample size of 18, a 2-sided 95% CI for the mean change from baseline in the low dose group will extend 1.14 on either side of the observed mean. To account for a 25% dropout rate, 50 subjects each will be enrolled in the VX-548 high dose, VX-548 mid dose, and the pregabalin groups; 25 subjects will be enrolled in the VX-548 low dose group. The total sample size is approximately 175 subjects.

The study is not powered for comparison between the VX-548 doses and the pregabalin reference arm.

12.2 Analysis Sets

The All Subjects Set is defined as all subjects who have been randomized or have received at least 1 dose of study drug. This analysis set will be used in subject listings, unless otherwise specified, and the disposition summary table.

The Full Analysis Set (FAS) is defined as all randomized subjects who have received at least 1 dose of study drug. The FAS is to be used to summarize subject demographics and baseline characteristics, and for all efficacy analyses, unless otherwise specified. Subjects will be analyzed according to the treatment to which they were randomized.

The Safety Set is defined as all subjects who have received at least 1 dose of study drug. The Safety Set is to be used for all safety analyses in which subjects will be analyzed according to the treatment they received, unless otherwise specified.

12.3 Statistical Analysis

12.3.1 General Considerations

All individual subject data for subjects who were randomized or received at least 1 dose of study drug will be presented in individual subject data listings.

Continuous variables will be summarized using the following descriptive summary statistics: the number of subjects (n), mean, SD, median, minimum value (min), and maximum value (max).

Categorical variables will be summarized using counts and percentages.

Baseline values for the NPRS daily pain intensity scores and DSIS will be defined as the average score from Day -7 to Day -1. For ECGs, the baseline value will be defined as the average of the non-missing pretreatment measurements (triplicate) on Day 1. For all other variables, baseline values will be defined as the most recent non-missing measurement collected before the first dose of study drug.

Change (absolute change) from baseline will be calculated as post-baseline value – baseline value.

Treatment-emergent (TE) period will include the time period starting from the date of the first dose of study drug to either (1) the Safety Follow-up Visit, (2) the ETT Visit if it replaces the Safety Follow-up Visit, or (3) 14 days after the last dose date for subjects who do not have a Safety Follow-up Visit or equivalent. The TE Period will be used for safety analyses unless specified otherwise.

12.3.2 Background Characteristics

Subject disposition, demographic and baseline characteristics, prior and concomitant medications, exposure, compliance, and important protocol deviations will be summarized.

12.3.3 Efficacy Analysis

All efficacy endpoints will be analyzed based on the FAS. Only the principal features of the efficacy analysis will be presented in this section. Details of all analyses will be provided in the SAP.

12.3.3.1 Analysis of Primary Endpoint

The primary efficacy endpoint is the change from baseline in the weekly average of the daily pain intensity on an NPRS at Week 12. The primary analysis will be a within-group comparison in any VX-548 dose group.

The primary efficacy analysis will be based on a mixed-effects model for repeated measures (MMRM), with change from baseline in weekly average of daily pain intensity score as the dependent variable; and fixed effects of treatment group, time (categorical), treatment group-by-time interaction, baseline weekly average of daily pain intensity, baseline weekly average of daily pain intensity-by-time interaction. The least squares (LS) mean change from baseline at Week 12 for each group will be presented with the corresponding SE and the corresponding 95% CI and *P* value.

12.3.3.2 Analysis of Secondary Efficacy Endpoints

The proportion of subjects with \geq 30% reduction from baseline in the weekly average of daily pain intensity on the NPRS at Week 12 will be summarized descriptively by treatment group and analyzed using the Cochran-Mantel-Haenszel test (stratified by sex and BMI). The proportion of subjects with \geq 50% and \geq 70% reduction from baseline will be analyzed similarly.

The proportion of subjects categorized as much improved or very much improved at Week 12 on the PGIC assessment will be summarized descriptively by treatment group and analyzed using the Cochran-Mantel-Haenszel test (stratified by sex and BMI).

The change from baseline in the weekly average of the DSIS at Week 12 will be analyzed similarly to the primary endpoint.

12.3.3.3 Multiplicity Adjustment

There is no multiplicity adjustment for this Phase 2 study.

12.3.4 Safety Analysis

The overall safety profile of VX-548 will be assessed in terms of the following safety and tolerability endpoints:

- Incidence of treatment-emergent AEs
- Clinical laboratory values
- Standard 12-lead ECG outcomes
- Vital signs
- C-SSRS

Safety endpoints will be analyzed based on the Safety Set. No statistical testing will be conducted. All safety data will be presented in individual subject data listings. Additional details will be provided in the SAP.

12.4 Interim Analysis

Not applicable.

12.5 Data Monitoring Committee Analysis

Not applicable.

12.6 Clinical Pharmacology Analysis

12.6.2 /Pharmacodynamic Analysis

A population analysis of plasma concentration versus time data of VX-548 and M6-548 may be performed using the nonlinear mixed-effects modeling approach. A population approach may also be used to investigate the exposure-response relationship for the efficacy and safety variables. A more detailed description of the methodology to be followed will be presented in the modeling and simulation analysis plan (MSAP). The results of the population and analysis (if done) will be reported in a separate document.

13 PROCEDURAL, ETHICAL, REGULATORY, AND ADMINISTRATIVE CONSIDERATIONS

13.1 Adverse Event and Serious Adverse Event Documentation, Severity Grading, and Reporting

13.1.1 Adverse Events

13.1.1.1 Definition of an Adverse Event

An AE is defined as any untoward medical occurrence in a subject during the study; the event does not necessarily have a causal relationship with the treatment. This includes any newly occurring event or worsening of a pre-existing condition (e.g., increase in its severity or frequency) after the ICF is signed.

An AE is considered serious if it meets the definition in Section 13.1.2.1.

13.1.1.2 Clinically Significant Assessments

Study assessments including laboratory tests, ECGs, PEs, and vital signs will be assessed and those deemed to have clinically significant worsening from baseline will be documented as an AE. When possible, a clinical diagnosis for the study assessment will be provided, rather than the abnormal test result alone (e.g., urinary tract infection, anemia). In the absence of a diagnosis,

the abnormal study assessment itself will be listed as the AE (e.g., bacteria in urine or decreased hemoglobin).

An abnormal study assessment is considered clinically significant if the subject has 1 or more of the following:

- Concomitant signs or symptoms related to the abnormal study assessment
- Further diagnostic testing or medical/surgical intervention
- A change in the dose of study drug or discontinuation from the study

Repeat testing to determine whether the result is abnormal, in the absence of any of the above criteria, does not necessarily meet clinically significant criteria. The determination of whether the study assessment results are clinically significant will be made by the investigator.

A laboratory value that is Grade 4 will not automatically be an SAE. A Grade 4 laboratory value will be an SAE if the subject's clinical status indicates a life-threatening AE.

13.1.1.3 Documentation of Adverse Events

All AEs will be collected from the time the ICF is signed until the following times:

- For subjects who do not enroll: until time of screen failure (e.g., screen failure, withdrawal of consent)
- For enrolled subjects who have a Safety Follow-up Visit: through the Safety Follow-up Visit
- For enrolled subjects who do not have a Safety Follow-up Visit, the earliest of
 - o 14 days after the last dose of tablet study drug, or
 - o the ETT Visit, if that visit is 14 days or later following the last dose of tablet study drug (see Section 9.1.4).

All subjects will be queried, using nonleading questions, about the occurrence of AEs at each study visit. When possible, a constellation of signs and/or symptoms will be identified as 1 overall event or diagnosis. All AEs for enrolled subjects will be recorded in the CRF and source document. AEs for subjects who are screened but not subsequently enrolled will be recorded only in the subject's source documents. The following data will be documented for each AE:

- Description of the event
- Classification of "serious" or "nonserious"
- Date of first occurrence and date of resolution (if applicable)
- Severity
- Causal relationship to study drug(s)
- Action taken
- Outcome
- Concomitant medication or other treatment given

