9.1.4 Early Termination of Treatment

If a subject prematurely discontinues study treatment, an Early Termination of Treatment (ETT) Visit should be scheduled as soon as possible after the subject decides to terminate study treatment; the subject will be encouraged to complete the capsule (pregabalin reference or matched placebo) study drug taper.

Subjects who prematurely discontinue treatment will be encouraged to stay in the study, including completing the daily diaries and returning for clinical visits to complete study efficacy assessments (i.e., NPRS, PGIC, DSIS, use of rescue medication, b. These subjects will also be required to complete the Safety Follow-up Visit, approximately $14 (\pm 2)$ days after their last tablet dose of study drug. The assessments performed at the Safety Follow-up Visit are listed in Table 3-2.

If the ETT Visit occurs 14 days or later following the last tablet dose of study drug, then the ETT Visit will replace the Safety Follow-up Visit, and a separate Safety Follow-up Visit will not be required. If the ETT Visit is within a week of any scheduled visit in the Treatment Period, it will replace that scheduled visit, and a separate visit will not be required.

If a subject withdraws consent for the study, no further assessments will be performed. Vertex may retain and continue using the study data and samples after the study ends, and may use the samples and information in the development of the study compound, for other drugs and diagnostics, in publications and presentations, and for educational purposes. If a subject withdraws from the study, the study data and samples collected will remain part of the study (Section 9.10).

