9.4 Study Restrictions

Study restrictions are summarized in Table 9-2. A non-exhaustive list of study restrictions will be provided in the Study Reference Manual.

Table 9-2 Study Restrictions

| Restricted | Timing of Restriction | | |
|---|--|--|--|
| Medication/Food/Activity a | Start | Stop | |
| Other investigational drugs or devices | 30 days before first dose of study drug, 5 half-lives before first dose of study drug, or time determined by local requirements (whichever is longer) | Completion of SFU assessments | |
| Any opioid use for chronic (including neuropathic) pain; for acute use, refer to Section 8.2 and Section 11.5.2 | 3 months before Screening Visit 1 | Completion of Week 12 or ETT Visit assessments | |
| Marijuana or marijuana products | 14 days before first dose of study drug | Completion of Week 12 or ETT Visit assessments | |
| Pregabalin (except use of reference study drug) and gabapentin | 14 days before first dose of study drug | Completion of study drug taper (i.e., 7 days after Week 12 or ETT Visit) | |
| Capsaicin patch | 90 days before first dose of study drug | Completion of Week 12 or ETT Visit assessments | |
| Lamotrigine, carbamazepine, oxcarbazepine, phenytoin, topiramate, valproic acid, mexiletine, and topical agents being prescribed for pain control | 14 days before first dose of study drug | Completion of Week 12 or ETT Visit assessments | |

Table 9-2 Study Restrictions

| Restricted | Timing of Restriction | | |
|--|--|---|--|
| Medication/Food/Activity a | Start | Stop | |
| All SNRIs and tricyclic antidepressants | 14 days before first dose of study drug | Completion of Week 12 or ETT Visit assessments | |
| All other treatments for pain, except acetaminophen (500 mg) and study drug (as outlined in Section 9.4.1), including nonpharmaceutical interventions | 14 days before first dose of study drug | Completion of Week 12 or ETT Visit assessments | |
| Oral steroids | 5 half-lives or 2 days (whichever is longer) before first dose of study drug | Until last dose of study drug is taken | |
| Medications, herbal and dietary supplements (including St. John's wort) known to be moderate or strong inducers of CYP3A | 14 days before first dose of study drug | Completion of SFU assessments | |
| Proton Pump Inhibitors | 72 hours before first dose of study drug | Until last dose of study drug is taken | |
| H2 blockers | 12 hours before each morning dose of study drug | 6 hours after each morning dose of study drug | |

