# **9 STATISTICAL ANALYSIS**

## **9.1 General Considerations**

The Schedule of Assessments is provided in Section 3 of the CSP. The precision standards for reporting variables are provided in an internal Biometrics document that specifies the programming rules including the precision for derived variables.

All individual subject data for subjects who were randomized or received at least 1 dose of study drug will be presented in individual subject data listings.

**Continuous variables** will be summarized using the following descriptive summary statistics: the number of subjects (n), mean, standard deviation (SD), median, minimum value (min), and maximum value (max), unless otherwise specified.

**Categorical variables** will be summarized using counts and percentages.

**Baseline value:** The baseline for the weekly average of NPRS and DSIS will be defined as average of the non-missing scores from Day -7 to Day -1. For the weekly average of NPRS, baseline values will be calculated if there are at least 4 non-missing scores. For weekly average of DSIS, baseline values will be calculated if there are at least 3 non-missing scores. For ECGs, the baseline values will be defined as the most recent average of non-missing triplicate measurements collected before the first dose of the study drug. For all other variables, baseline values will be defined as the most recent non-missing measurement collected before the first dose of study drug, unless otherwise specified.

**Change (absolute change) from baseline** will be calculated as post-baseline value – baseline value.

**Treatment-emergent (TE) Period** will include the time period from the date of the first dose of study drug to either (1) the Safety Follow-up Visit, (2) the ETT Visit if it replaces the Safety Follow-up Visit, or (3) 14 days after the last dose for subjects who do not have a Safety Follow-up Visit or equivalent.

**Unscheduled visits:** Unscheduled visit measurements will be included in the analysis as follows:

- In scheduled visit windows per specified visit windowing rules
- In the derivation of baseline
- In the derivation of maximum and minimum values during the TE period, and maximum and minimum change from baseline values during the TE period for safety analyses
- In individual subject data listings as appropriate

**Visit windowing rules:** The analysis visit windows for protocol-defined visits are provided in [Appendix A](#).

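### For subjects without a Safety Follow-up Visit, the stop date for AE collection is the earlier of two dates, one of which can never be the earlier, so collection can end before the treatment-emergent period does

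*Protocol*

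**What the plan says.** Protocol 13.1.1.3 gives the end of AE collection for three kinds of subject. The third rule reads "For enrolled subjects who do not have a Safety Follow-up Visit, the earliest of" two dates. The first is "14 days after the last dose of tablet study drug, or" and the second is "the ETT Visit, if that visit is 14 days or later following the last dose of tablet study drug". The same section says that every subject is asked about AEs at each study visit.

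Protocol 9.1.4 says when an ETT Visit stands in for the Safety Follow-up Visit: "If the ETT Visit occurs 14 days or later following the last tablet dose of study drug".

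Protocol 12.3.1 ends the TE period at the Safety Follow-up Visit; or at "2) the ETT Visit if it replaces the Safety Follow-up Visit"; or at "14 days after the last dose date for subjects who do not have a Safety Follow-up Visit or equivalent". SAP 9.1 has the same three parts, the last worded "14 days after the last dose for subjects who do not have a Safety Follow-up Visit or equivalent". Neither limits the last dose to tablets.

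Protocol 9.1.3 and 9.6 stop the tablets at Week 12 and continue the capsule study drug through a 7-day taper. After early discontinuation the taper is encouraged (9.1.4).

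**The concern.** The collection rule and the TE period should end on the same date for each subject. For subjects without a Safety Follow-up Visit they can differ, for two separate reasons: the rule takes the earlier date where only the later one makes sense, and it counts from the last tablet where the TE definition counts from the last dose.

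Safety and tolerability are a primary objective, and SAP 9.4.1 counts treatment-emergent AEs through the end of the TE period. Days inside that period on which the protocol no longer requires collection can lower the count without showing as missing data. Sites may also differ in practice, because the cut-off conflicts with the instruction to ask about AEs at every visit.

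**Working it through.** Count days from the last tablet (day 0). Let e be the day of the ETT Visit and k the number of days from the last tablet to the last capsule.

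**Inputs**
- AE collection end without a Safety Follow-up Visit: min(14, e), with e used only if e ≥ 14; otherwise 14 (Protocol 13.1.1.3).
- ETT Visit replaces the Safety Follow-up Visit if e ≥ 14 (Protocol 9.1.4).
- TE end: e if the ETT Visit replaces the Safety Follow-up Visit; 14 days after the last dose if there is no such visit (Protocol 12.3.1, SAP 9.1).
- Taper: 4 days plus 3 days, starting the day after the Week 12 Visit, with no tablets (Protocol 9.6, 9.1.3).

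**The plan's own timeline.** The taper lasts 4 + 3 = 7 days. The Safety Follow-up Visit is 7 (± 2) days later, so on day 7 + 7 = 14, range 12 to 16. This reproduces the 14 ± 2 days in Protocol 9.1.3. Subjects who attend that visit have no gap, because both windows end there.

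**Step 1: the ETT limb.** Since e ≥ 14 whenever the limb applies, min(14, e) = 14 in every case. At e = 14 the two dates tie; the limb never moves the date.

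**Step 2: a late ETT Visit replaces the Safety Follow-up Visit.** Gap = TE end − collection end = e − 14.

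| ETT day e | Collection ends | TE period ends | Days uncovered |
|---|---|---|---|
| 14 | 14 | 14 | 0 |
| 21 | 14 | 21 | 7 |
| 28 | 14 | 28 | 14 |
| 35 | 14 | 35 | 21 |

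This gap does not depend on how tablets and capsules are treated.

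**Step 3: no Safety Follow-up Visit and no ETT Visit that replaces it.** Collection ends on day 14. If the last dose includes capsules, the TE period ends on day 14 + k, so the gap is (14 + k) − 14 = k days. With no capsule after the last tablet, k = 0 and there is no gap. With a full taper starting the day after the last tablet, k = 7: the TE period ends on day 21 and 7 days are uncovered.

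That start date is stated only for the Week 12 Visit. For early discontinuers, Protocol Table 9-2 times the end of the taper as "Completion of study drug taper (i.e., 7 days after Week 12 or ETT Visit", so k is not fixed at 7 for them.

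**Step 4: effect of taking the later date.** max(14, e) = e for every e ≥ 14, so the Step 2 gap becomes 0 (checked at e = 14, 21 and 28). The Step 3 gap stays at k until the two anchors agree.

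**The case against.** The strongest reply is that the reach is narrow. Protocol 9.1.4 requires early discontinuers to complete the Safety Follow-up Visit, and Table 3-2 shows AE review as continuous through it. A site that sees a subject at a late ETT Visit would ask about AEs in any case. Serious AEs have their own rule in Protocol 13.1.2.2, and those judged related remain reportable after the Safety Follow-up Visit. All of this stands. It limits the loss mainly to non-serious AEs in subjects with a late ETT Visit or a missed required visit. It does not make the rule right, since asking at a late ETT Visit is what the cut-off says is no longer needed.

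It can also be said that the tablet-versus-dose gap is an inference, because neither TE definition names capsules. That is fair. Including them is still the plain reading: the capsules are called study drug, 13.1.1.3 says tablet where 12.3.1 and SAP 9.1 do not, and SAP 9.2.5 states a limit to the treatment period where it wants one.

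A reader might go further in three ways that the documents do not support.
- **Unequal arms.** Active pregabalin is in the capsules, so after the taper that arm has 7 days of follow-up after its last active dose, against 14 for VX-548. The visit schedule produces this for everyone who completes the taper and attends follow-up (Protocol 9.1); 13.1.1.3 does not cause it.
- **A large share of the TE period lost.** Seven uncovered days out of 21 is a share of the post-tablet tail only. The TE period starts at the first dose; for a 12-week completer it is about 84 + 21 = 105 days, and 7/105 is about 7%.
- **A count of affected subjects.** The 25% dropout figure is a sample-size assumption. The documents give no rate of missed Safety Follow-up Visits or late ETT Visits, so no count follows.

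**Conclusion.** Wrong as written, minor. The ETT limb in Protocol 13.1.1.3 can never operate. Where a late ETT Visit replaces the Safety Follow-up Visit, e − 14 days of the TE period have no required AE collection; this follows from the text alone. Where there is neither visit, up to 7 days are uncovered, on two assumptions: that the last dose includes taper capsules, and that the taper starts the day after the last tablet.

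Not every subject without a Safety Follow-up Visit has a gap: there is none if the ETT Visit falls on day 14 or, with neither visit, if no capsule follows the last tablet. The number affected is unknown and probably small. The primary efficacy analysis and the sample size are untouched.

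**What to change.** In Protocol 13.1.1.3, replace *earliest* with *latest*, and leave the ETT limb keyed to the last tablet so that it still matches 9.1.4. Alternatively, replace the rule with the three-part TE end definition from Protocol 12.3.1.

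In either case, reconcile the last-tablet and last-dose anchors across Protocol 9.1.4, 12.3.1 and 13.1.1.3 and SAP 9.1, and state whether the last dose includes taper capsules, so that AE collection and the TE period end on the same date. The choice of anchor is the sponsor's. Putting any study drug into the ETT limb alone would create a new mismatch. For example, with a taper ending on day 7 and an ETT Visit on day 16, that visit replaces the Safety Follow-up Visit under 9.1.4 and ends the TE period. It is only 9 days after the last capsule, so the altered limb would not be met and collection would run to day 7 + 14 = 21.

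The cost is a wording amendment and some extra days of AE collection in a few subjects.
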